Co-investigators [name] and [name] have collaborated on a research project that examined occurrence and frequency of recovery of genetically identical VRE strains at the MD Anderson Cancer Center. Both time between isolation of an identical strain and location of isolation of the identical strain were determined. Of the 82 VRE transmissions, 32.9% were repetitions of genetically identical strains. The average time between the reoccurrence of a strain was 49 days [median: 36, range: 0-183 days]. One strain reoccurrence was in the same room as the previous occurrence of the strain, 6 were in the same pod, 14 were on the same floor and 6 were on a different floor. Twelve of the reoccurrences were from patients on the leukemia floors, 10 were on the hematopoietic stem cell transplant unit and 5 were between these services.³³

Epidemiology and Prevention of eiHAIs at DMC The PI ([name]) on this proposal is the Medical Director of Infection Prevention and Hospital Epidemiology at DMC and oversees all infection control activities at study hospitals. The PI has published extensively at DMC on hospital-acquired infections, including VRE,³⁴ MRSA,³⁵ ESBLs,³⁶ *A. baumannii*³⁷ and *C. difficile*³⁸. Clearly these eiHAI pathogens are a persistent problem at the study sites. The PI's research and infection control teams have notable experience in controlling the spread of these pathogens in the hospital. Because of the strong infection control infrastructure already in place at the study sites, it is highly likely that the PX-UV disinfection and sham device interventions will proceed successfully on study units.

RESEARCH DESIGN AND METHODS

Study overview

We will conduct a prospective, double-blind, two-armed crossover clinical trial with an initial intervention period of 12 months, followed by a 6-month washout period and a second intervention period of 12 months. The 6-month washout period will be necessary because of the long-term survivability of eiHAs, such as *C. difficile*, on environmental surfaces.

Sample size estimation

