For the 16 units to be studied, over 8 months from December 2014 through July 2015, the average rate of *C. difficile* infections on day 4+ of a patient's hospital stay was 1.3 per 1000 days. Rates of ESBL+VRE+ MRSA + *A. baumannii* are 1.5 times that for *C. difficile*, so the total rate of all four infection types would be 3.2 (=1.3x2.5). The total average daily census on the 16 units was 291. Assuming the average patient stay is 5.2 days, 42.3% of patient days will be day 4+, so the expected number of daily eligible patient days would be 123. For 24 months of intervention the total number of eligible days would be $123 \times 730 = 89,790$, or 44,895 per arm.

If the power for the Poisson model is approximated by that for a binomial test of proportions, and with a final alpha level of 0.049 to take into account one interim analysis, a 31% reduction in eiHAI incidence (from 3.2 to 2.208 per 1000 eligible days) would be detectable with 81% power.

Hospital Unit Selection

Patient care units from two healthcare facilities have been identified for this study based on a relatively high average recovery of eiHAs. These units will be randomized to receive either the intervention or sham PX-UV devices in Phase 1 of the study, and the intervention and sham PX-UV devices will switch in Phase 2 of the study. The protocol for use of the devices is outlined below.

Clinical Sites

Two DMC acute-care hospitals are being proposed for this project, Sinai-Grace Hospital (SGH) and Detroit Receiving Hospital (DRH). SGH is a 383-bed hospital, and DRH is a 248-bed hospital. The study will be conducted in eight hospital units in SGH and eight hospital units in DRH, including two medical intensive care units (ICUs), two surgical ICUs and 12 non-ICU medical-surgical wards. The 16 study units include a total of 379 beds. During the 24-month study intervention period, we anticipate that 40,852 total patients will be cared for on study units accounting for 89,790 eligible patient days out of a total of 212,430 patient days. If past experience continues unchanged, during the 24-months of intervention, 287 eiHAs attributable to these units would be observed.

Devices will be deployed on these study units with the sham and intervention devices split evenly between SGH and DRH. Within each study site, the types of devices (PX-UV vs sham) will be assigned randomly to the units in Phase 1 and then switched in Phase 2.

Patient Selection

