Analyzing the isolate to library: The isolate sequencing will be interpreted by an experienced microbiologist who will be masked to all clinical, epidemiological and microbiological study information. A reference isolate will be defined initially to compare subsequent isolates to the reference isolates for mapping the clonal spread of an isolate. The genome data will be analyzed to identify single-nucleotide polymorphisms (SNPs) and insertions or deletions. Then reference isolates will be compared to subsequent isolates for mapping clonality of the isolates to define the strain relatedness, and to define any repetition of a particular strain over a given period of time. Further, we can also define if an intervention such as pulsed-xenon disrupts the repetition pattern of strains and compare it other intervention such as manual disinfection.

Statistical Analysis

Aim 1. The primary analysis will use a Poisson regression model to compare PX-UV disinfection with sham disinfection. Analysis will begin with testing for a carryover effect, but the long 6-month washout is expected to make carryover unlikely. An interim analysis for efficacy will be made after the first 12-month intervention period using an O'Brien-Flemming boundary, the trial may be halted for efficacy if a chi square statistic of 8.78 or greater is observed for the interim test ($p \leq 0.003$). With the interim analysis, the p-value for the test at end of the study will need to be 0.049 or lower to be significant. The primary regression model will include patient age, sex, race and indicator variables for co-morbid conditions. Secondary analysis will summarize and compare study arms (and periods) on: administered antibiotic doses and types, hand hygiene compliance, room cleanliness quality (monitoring through fluorescent marking) and eiHAI colonization pressure.

Aim 2 The frequencies of genetically identical strains of eiHAIs in the selected units will be summarized descriptively with regards to timing, location and clinical strain characteristics.

Study Timeline

ACTIVITY TO ADDRESS STUDY AIMS	Year 1				Year 2				Year 3				Year 4				Year 5	
Quarter	1	2	3	4	1	2	3	4	1	2	3	4	1	2	3	4	1	2
IRB, training of environmental services staff	X	X	X	X		X				X				X				X
Phase 1 of crossover			X	X	X	X												
Wash-out period							X	X										
Phase 2 of crossover									X	X	X	X						
Laboratory analysis						X	X	X					X	X	X			
Data analysis and manuscript preparation									X	X	X			X	X	X	X	X

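### Units are randomised, but the primary Poisson test and the 81% power treat patient-days as independent, and the interim boundary is applied before any unit has crossed over

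*Combined protocol and SAP*

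**What the plan says.** **Randomisation.** Under Clinical Sites, within each hospital "the types of devices (PX-UV vs sham) will be assigned randomly to the units in Phase 1 and then switched in Phase 2". There are 16 units in two hospitals, "including two medical intensive care units (ICUs), two surgical ICUs and 12 non-ICU medical-surgical wards". No stratification by unit type is described.

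**Primary analysis.** Statistical Analysis, Aim 1, names a Poisson regression comparing PX-UV with sham, preceded by a carryover test, and then says "The primary regression model will include patient age, sex, race and indicator variables for co-morbid conditions". No unit or period term, random effect, robust variance, dispersion parameter or unit-level test is stated there or elsewhere. Negative binomial regression appears only in the account of an earlier *C. difficile* study.

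**Power.** Sample size estimation begins "If the power for the Poisson model is approximated by that for a binomial test of proportions" and concludes that "a 31% reduction in eiHAI incidence (from 3.2 to 2.208 per 1000 eligible days) would be detectable with 81% power", with 44,895 eligible days per arm and a final alpha of 0.049. It gives no intracluster correlation, CV or design effect.

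**Interim.** "An interim analysis for efficacy will be made after the first 12-month intervention period", and "the trial may be halted for efficacy if a chi square statistic of 8.78 or greater is observed for the interim test".

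**The concern.** When units are randomised, the standard error has to reflect how unit rates vary. A plain Poisson model on patient-days counts only Poisson noise. Two kinds of extra variation have different consequences here.

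1. **Final analysis.** Stable differences between units cancel because each unit is seen under both devices. Changes in a unit's rate from one phase to the other, such as an outbreak or a strain cluster, do not cancel, and the model-based standard error leaves them out. The test then rejects too often, the interval is too narrow, and a valid analysis has less than the stated power.
2. **Interim analysis.** Only phase 1 is available, so the arms are made up of different units. Stable differences, for example between ICUs and wards, go straight into the comparison, and the trial could be stopped for efficacy before the within-unit comparison exists.

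The protocol's own preliminary data give a reason to expect clustering in time and place: "Of the 82 VRE transmissions, 32.9% were repetitions of genetically identical strains".

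**Working it through.** **Inputs.** From Sample size estimation: rates of 3.2 and 2.208 per 1000 eligible days, 44,895 days per arm, alpha 0.049. From Clinical Sites: 16 units, of which 4 are ICUs and 12 are wards. From Statistical Analysis: a chi-square boundary of 8.78 after phase 1. All CVs below are assumptions.

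**1. The plan's own figures.** A two-sided test of two proportions with p1 = 0.0032, p2 = 0.002208, n = 44,895 per arm and critical value 1.9685 has power 81.4%. This matches the stated 81% and uses independent days. A chi-square of 8.78 on 1 df gives p = 0.00305, so the boundary is correct for independent data.

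**2. Events per unit and phase.** 44,895 × 0.0032 = 143.7 and 44,895 × 0.002208 = 99.1. Divided by 16, m0 = 8.98 and m1 = 6.20.

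**3. Final analysis with unit-by-period CV k.**

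- Var(log RR) = [1/m0 + 1/m1 + 2k²]/16. The standard error is 0.131, 0.135, 0.149 and 0.168 at k = 0, 0.10, 0.20 and 0.30.
- Power follows from |log 0.69| = 0.371 divided by that standard error, with a normal or a noncentral t (14 df) reference.
- Type I error of the plain Poisson test = 2[1 − Φ(1.9685/√(1 + 8.98k²))].

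| k (assumed) | Type I error | Power, normal | Power, t(14) | Reduction detectable at 81%, normal / t(14) |
|---|---|---|---|---|
| 0 | 4.9% | 81% | 75% | 31% / 33% |
| 0.10 | 5.9% | 78% | 72% | 32% / 34% |
| 0.20 | 9.1% | 70% | 64% | 35% / 37% |
| 0.30 | 14.3% | 59% | 53% | 39% / 41% |

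The 6 points lost at k = 0 come from the t reference, not from variation.

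Simulation (equal days per unit, no covariates, 4 of 8 units per arm in each hospital, stable CV 0.3) gave 6.0-6.1%, 9.2-9.4% and 14.6-15.0% at k = 0.10, 0.20 and 0.30. Adding unit and period indicators to the Poisson model left these at 6.0-6.1%, 9.1-9.4% and 14.5-14.8%. A unit-level t test on 14 df stayed at 4.5-4.8%. A stable CV of 0.3 or 0.5 with k = 0 left the final plain Poisson test at 4.7-4.9%.

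**4. An illustration of k.** In Recovery of Genetically Identical VRE Strains, 0.329 × 82 = 27 repeats: 1 in the same room, 6 in the same pod, 14 on the same floor and 6 on another floor. Suppose r = 7 (room and pod) or r = 21 (adding floor) were same-unit pairs. Variance inflation is then 1 + 2r/82 = 1.17 or 1.51. If only the non-*C. difficile* share of events, 1.5/2.5 = 60%, clusters in this way, inflation is 1.10 or 1.31. With k = √((inflation − 1)/8.98), k is 0.11 or 0.19 and type I error is 6.1% or 8.5%. This is VRE at a different centre, so it illustrates and does not estimate.

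**5. Interim under no treatment effect.** Share of simulated trials with chi-square of 8.78 or more:

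| Stable differences between units (assumed) | Boundary crossed |
|---|---|
| None | 0.3% |
| CV 0.1 | 0.4% |
| CV 0.3 | 2.3-2.7% |
| CV 0.5 | 9.1-9.8% |
| ICU rate 1.5 / 2 / 3 times ward rate | 1.1% / 4.5% / 16% |

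Half of these crossings favour PX-UV. The ICU rows assume two ICUs and six wards per hospital. Counting a rejection at either look, overall error is 6.9% at CV 0.3 and 13.5% at CV 0.5. Counting only interim crossings that favour PX-UV, plus final rejections in either direction, it is 5.9% and 9.2%.

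**The case against.** The strongest reply is that the plan is incomplete rather than wrong. The covariate sentence need not be exhaustive; Use of crossover design and Aim 1.2 show that a within-unit comparison is intended; and the carryover test needs sequence and period structure. That is fair as to intent, but unit and period terms in a plain Poisson model leave the error rate where it was (step 3), so the gap in the variance remains.

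Second, every CV is assumed. The illustration reaches only 0.11-0.19, and its upper end treats one floor as one unit, so the CV 0.30 row is a sensitivity extreme. This stands, and it limits the claim about size.

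Third, the simulations carry no covariates. Age and co-morbidity terms could absorb some of the ICU-ward difference. The plan also collects monthly unit-level data on hand hygiene, cleaning quality and colonization pressure, but it uses them in secondary comparisons. This too affects the size, not the existence, of the problem.

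Fourth, the interim rates are two-sided, the wording is that the trial may be halted, and at a stable CV of 0.1 the boundary barely moves. Units were also chosen for relatively high recovery of these organisms, which may narrow their spread. All true, but nothing in the plan keeps the CV that low, and ICUs and wards are mixed.

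**Conclusion.** The concern holds and needs correcting before analysis. The stated primary test and the power calculation share one assumption, independent patient-days, and the unit-level randomisation does not support it. The omission is certain; the size of the harm is conditional. At an unit-by-period CV of 0.10 to 0.20, close to the range of the VRE illustration, the final test runs at about 6% to 9% instead of 4.9%, and a valid test has 78% to 70% power (72% to 64% with t on 14 df). At CV 0.30 the figures are 14-15% error and 59% (53%) power. Stable unit differences do not harm the final test. They do harm the interim, where a stable CV of 0.3 to 0.5 raises the crossing rate from 0.3% to roughly 2.5% to 9.5%, half of it towards PX-UV. These figures assume equal days per unit and no covariate adjustment.

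**What to change.** **Primary analysis.** State inference at the level of randomisation, allowing unit-by-period variation and using a small-sample reference. Choose one in advance:

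- a two-stage analysis: patient-level Poisson on age, sex, race and co-morbidities gives expected events per unit and phase, followed by a period-adjusted within-unit comparison of observed with expected, using t on about 14 df and a stated rule for zero counts;
- a patient-level mixed Poisson model with period, unit and unit-by-period effects and a small-sample correction;
- a permutation test that follows the hospital-stratified randomisation.

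**Interim.** Apply the boundary to a between-unit test stratified by hospital, either on unit summaries or by permutation. If 4 of 8 units per hospital are in each arm, there are 70 × 70 = 4,900 allocations, so the smallest two-sided p is 2/4,900 = 0.0004 and 0.003 can be reached. The simpler alternative is to drop the efficacy look before crossover.

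**Power.** Describe 81% as the figure with no extra-Poisson variation, and give power or the detectable reduction over a stated CV range.

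**Cost.** SAP wording and a re-run calculation, with no new data. Stated power falls to about 75% at CV 0 with the 14-df reference, and to 72%, 64% or 53% at CV 0.10, 0.20 or 0.30. A valid between-unit interim would rarely stop the trial: for the planned 31% reduction its power is about 8% at CV 0 and 4% at a stable CV of 0.3, against about 16% for the plain Poisson test at CV 0.
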